3.2.1.2.4 Complete procedure

The proportion of complete procedure (defined as procedures (i.e. colonoscopies) that reached the caecum) will be assessed. It will be tabulated by treatment group using frequency count with two-sided 95 % CI and analysed using Cochran-Mantel-Hænszel (CMH) chi-square for the proportions adjusting for country effect. The general association statistic will be used to assess the test significance.

The SAS Freq procedure will be used as follows:

proc freq data=ADPR(where=(PRTRT='COLONOSCOPY' and AVISITN=2 and ITTFL='Y'));

```
table COUNTRYC*TRTP*PROCCUR / CMH;
```

run;

The difference of proportions with the 95 % CI and p-value will be summarised.

The reasons for non-completion will also be presented.

3.2.1.2.5 *Time to caecal intubation*

The time to caecal intubation (from colonoscope introduction to caecal intubation) will be assessed and will be analysed using survival methods on subjects who performed colonoscopy.

Table 8 specifies the event and censoring dates to be used in the analysis of time to clear effluent.

	· · · · ·	
Event	Time of event	Outcome
Caecal intubation	Time of caecal intubation	Event
Procedure (i.e. colonoscopy) did not reach the caecum	Time of withdrawal of colonoscope	Censored

Table 8Time to caecal intubation (minutes)

The distribution of time to caecal intubation will be estimated using the Kaplan-Meier (KM) product limit method. The results will be presented in a summary table and a KM plot will also be constructed.

The summary table will present by treatment group the numbers and percentages of subjects with occurrence of caecal intubation and the numbers and percentages of censored subjects. The summary will also include the median time to caecal intubation as well as the 25th and 75th percentiles with their two-sided 95 % CI, the percentage and 95 % CIs of subjects who had caecal intubation at 5, 10, 15, 20, 25, 30, 45 and 60 minutes from KM estimates.

Confidence intervals for median time to caecal intubation as well as the 25th and 75th percentile CIs will be calculated using the method of Brookmeyer and Crowley (1982) [5], which is the default method within SAS® version 9 and higher.

Kaplan-Meier curves will be constructed by treatment group and will display the number of subjects at risk at 5, 10, 15, 20, 25, 30, 45 and 60 minutes.

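### Censoring failed intubations at scope withdrawal makes the Kaplan-Meier percentages for time to caecal intubation too high; cumulative incidence should replace them

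*SAP*

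**What the plan says.** SAP 3.2.1.2.5 analyses time to caecal intubation by survival methods in subjects who had a colonoscopy. Table 8 has two rows. Reaching the caecum is the event. The other row, "Procedure (i.e. colonoscopy) did not reach the caecum", is censored at "Time of withdrawal of colonoscope".

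The summary table then gives, by arm:
- the "numbers and percentages of subjects with occurrence of caecal intubation" and "the numbers and percentages of censored subjects";
- the median and quartiles with confidence intervals;
- the percentage of "subjects who had caecal intubation at 5, 10, 15, 20, 25, 30, 45 and 60 minutes from KM estimates".

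A Kaplan-Meier plot and a Cox model adjusted for country follow on the same coding.

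The section just before it, SAP 3.2.1.2.4, handles completion separately: "The proportion of complete procedure (defined as procedures (i.e. colonoscopies) that reached the caecum) will be assessed". It gives the proportion by arm with a 95% CI, the difference with its CI, a country-adjusted Cochran-Mantel-Haenszel p-value and the reasons for non-completion. SAP 3.1.5 makes all secondary tests descriptive.

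**The concern.** Kaplan-Meier assumes that a censored subject would have gone on to have the event at the same rate as those still under observation. That cannot be so here: once the scope is out, the caecum will not be reached in that procedure. Removing failures from the risk set hands their probability to later successes. The result is labelled as the percentage of subjects who had caecal intubation, but it is not that percentage.

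Failure may also be related to treatment. Protocol 1.1 names incomplete examination as a consequence of inadequate preparation. If one arm has more incomplete procedures, its curve is raised more, and the contrast between arms in this table and plot is reduced. The same table could print a crude 90% intubated above a 60-minute figure several points higher.

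**Working it through.** **Inputs.** The documents give no completion rate, intubation time or withdrawal time, so there is no planned figure to reproduce on this point. From the SAP come the Table 8 coding, the display times and 125 randomised per arm (section 1.4.4). Everything else below is an assumption.

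**Formulas.**
- Kaplan-Meier: percentage intubated by t = 1 − ∏(1 − d/n) over event times up to t, where d is the number of events and n the number still at risk, with failures removed at withdrawal.
- Cumulative incidence: Table 8 has no censoring other than failure, so this is simply (number intubated by t) / (all scopes).

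**Hand example.** Assume 120 scopes, of which 108 reach the caecum (median 12 min, log SD 0.6, last success at 57 min) and 12 fail, all withdrawn at 20 min. By 20 min 87 are intubated, by 30 min 101, by 60 min 108.
- At 20 min both methods give 87/120 = 72.5%, leaving 33 at risk. The 12 failures then drop out, leaving 21.
- At 30 min, 14 of those 21 have been intubated. Kaplan-Meier gives 1 − (33/120)(7/21) = 90.8%; cumulative incidence gives 101/120 = 84.2%.
- At 60 min the last 7 have succeeded. Kaplan-Meier gives 100%; cumulative incidence gives 108/120 = 90.0%.
- If all 12 failures are withdrawn after the last success, the two methods agree exactly.

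**Sensitivity to withdrawal time.** Assume 90% completion, log-normal intubation times (median 10 min, log SD 0.5) and failures withdrawn uniformly over a window. The true percentage is 0.90 × Φ(ln(t/10)/0.5), which is 71.2% at 15 min, 88.7% at 30 and 90.0% at 60. Kaplan-Meier averages over 2,000 simulated arms of 125:

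| Failures withdrawn | 15 min | 30 min | 60 min |
|---|---|---|---|
| 20-60 min | 71.2% | 89.3% | 91.3% |
| 10-40 min | 71.7% | 92.0% | 96.3% |
| 5-20 min | 74.5% | 98.1% | 100.0% |
| True | 71.2% | 88.7% | 90.0% |

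For the 10-40 min window, true completion of 98 / 95 / 90 / 85% shows at 60 min as about 99.5 / 98.5 / 96.3 / 93.5%.

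**Quantiles (large-sample calculation).** With the 10-40 min window the median is essentially unchanged. The 75th percentile moves from 16.2 to 16.0 min at 90% completion and from 18.1 to 17.5 min at 85%. With 5-20 min and 85% completion it moves from 18.1 to about 15.9 min.

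**Arm difference at 60 min, 98% against 90% completion (true gap 8 points).** Kaplan-Meier shows 98.5 − 91.3 = 7.2 points for 20-60 min, 99.5 − 96.3 = 3.2 for 10-40 min, and 0 for 5-20 min.

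**Test of the arms.** A separate simulation used 120 per arm, 5% against 15% failures, median success 12 min, and an unadjusted log-rank test standing in for Cox. With median failed withdrawal at 8, 12, 20 and 40 min, the test on the Table 8 coding rejects in 6, 12, 28 and 49% of runs. With failures kept at risk past the last event it rejects in about 55%. A simple test of completion proportions, as a stand-in for section 3.2.1.2.4, rejects in 75-77%.

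**The case against.** A reader might infer that the plan conceals a difference in completion between arms. It does not. Section 3.2.1.2.4 compares completion directly, with interval, p-value and reasons, and in the simulation above a test of that kind was the most sensitive of the three. Under Table 8 the censored subjects are exactly the failures, so the crude completion rate also stands in the same table as the Kaplan-Meier percentages.

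A reader might also infer that the Cox model counts failures as successes. It does not. Censoring at withdrawal yields a cause-specific hazard ratio: the rate of intubation while the scope is in. That is a legitimate measure of speed, and the protocol listed this endpoint as duration of intubation, apart from completion. Its lower rejection rate above reflects a different question, not an invalid test. Under the 10-40 min assumptions with 98% against 90% completion, the hazard ratio is about 1.24 as planned and 1.29 with failures kept at risk.

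The size is also uncertain. SAP 3.2.1.2.6 measures examination from caecal intubation to scope withdrawal, which suggests that withdrawal means removal and not the moment when advance was given up. That would place failures later and reduce the bias. With few failures, or late ones, the effect is about a point or less, and early display times and the median barely move unless failures come out early.

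All of this stands and limits the point. None of it makes the Kaplan-Meier percentage equal to what its label says.

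**Conclusion.** The point holds as a minor correction to one descriptive secondary endpoint. The Kaplan-Meier percentages in SAP 3.2.1.2.5 overstate intubation whenever failed scopes are withdrawn before later successes, and the upper quantiles are affected too if failures are frequent. The direction follows from the coding alone. The size does not: at an assumed 90% completion, the 60-minute overstatement runs from about 1 point (withdrawal at 20-60 min) through about 6 (10-40 min) to 10 (5-20 min), and at 15 min it is 0.5 points or less in the first two cases. An arm difference is attenuated within this table and plot, but remains visible in section 3.2.1.2.4 and in the crude counts. The primary analysis and the sample size are untouched.

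**What to change.** In SAP 3.2.1.2.5, replace the Kaplan-Meier percentages, quantiles and plots (including those by country) with the cumulative incidence of caecal intubation, recoding the second row of Table 8 from censored to competing event. The final value then equals the crude percentage intubated in the same table, which is a useful programming check, and it no longer depends on when failed scopes came out. A quartile that the curve does not reach is reported as not reached.

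For the percentages only, keeping failures event-free past the last event time gives the same numbers. The planned number-at-risk display would then count subjects whose scope is already out, so cumulative incidence is the cleaner choice.

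Keep the Cox model, but label it a cause-specific hazard ratio for speed of intubation while the scope is in, to be read with section 3.2.1.2.4. If the comparison is meant to reflect the cumulative incidence, specify a subdistribution hazard model instead.

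Cost: one table row and one derivation, with the affected outputs rerun. No new data are needed.

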3.2.1.2.6 Duration of examination

The duration of examination (in minutes), measured by the difference between the time of caecum intubation and the time of withdrawal of the colonoscope, will be assessed. Subjects for whom the caecum was not reached will be excluded from this analysis. The results will be presented by treatment group using descriptive summary statistics (mean, SD, median, quartiles and ranges) and using a two-way ANOVA including treatment and country as well as the interaction between treatment and country, if it is significant (i.e. p < 0.10), as covariates using the following SAS code:

proc mixed data=ADCC(where=(PRTRT='COLONOSCOPY' and AVISITN=2 and ITTFL='Y'));

class TRTP COUNTRYC; model ADUREXA = TRTP COUNTRYC TRTP*COUNTRYC; lsmeans TRTP / diff cl;

run;

The adjusted mean durations of examination, the adjusted treatment difference with their 95 % CI and the p-value of difference will be summarised.

In addition, this analysis will also be produced per country so that mean durations and the estimated treatment differences will also be provided per country using the following SAS code.

proc mixed data=ADCC(where=(PRTRT='COLONOSCOPY' and AVISITN=2and ITTFL='Y'));

```
class TRTP COUNTRYC;
model ADUREXA = TRTP COUNTRYC TRTP*COUNTRYC;
lsmeans TRTP*COUNTRYC / diff cl;
```

run;

3.2.1.2.7 Rescue treatment

The proportion of procedures that need a rescue treatment (saline enema) because of inadequate preparation intake will be assessed. It will be tabulated by treatment group using frequency count with two-sided 95 % CI and analysed using Cochran-Mantel-Hænszel (CMH) chi-square for the proportions adjusting for country effect. The general association statistic will be used to assess the test significance.

The SAS Freq procedure will be used as follows:

```
proc freq data=ADCM(where=(CMCAT='RESCUE MEDICATION' and CMTRT='ENEMA' and ITTFL='Y'));
table COUNTRYC*TRTP*CMOCCUR / CMH;
```

run;

The difference of proportions with the 95 % CI and p-value will be summarised.

3.2.1.2.8 Need for a nasogastric tube

The proportion of subjects who needed a nasogastric tube to complete preparation will be assessed and the reason for placing it will be collected. They will be tabulated by treatment group using frequency count with two-sided 95 % CI and analysed using Cochran-Mantel-Hænszel (CMH) chi-square for the proportions adjusting for country effect. The general association statistic will be used to assess the test significance.

The SAS Freq procedure will be used as follows:

```
proc freq data=ADEX(where=(EXTRT=' EZICLEN/IZINOVA' and ITTFL='Y'));
table COUNTRYC*TRTP*NASOTUBE / CMH;
```

run;

The difference of proportions with the 95 % CI and p-value will be summarised.

The proportion of subjects who needed a nasogastric tube to complete preparation will also be tabulated by dose.

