26	3.2.1.2.4	18JUN2018	26FEB2020	The reason for non-completion will also be
		(v2.0)	(v3.0)	described.
27	3.2.1.2.5	18JUN2018 (v2.0)	26FEB2020 (v3.0)	The times for KM estimates have been revised (e.g. addition of 15h and 18h for time to clear effluent) to be more consistent.
29	3.2.1.2.8	18JUN2018 (v2.0)	26FEB2020 (v3.0)	The proportion of subjects who needed a nasogastric tube to complete preparation will also be tabulated by dose, in addition of overall summary.
29	3.2.1.2.9	18JUN2018 (v2.0)	26FEB2020 (v3.0)	The overall treatment acceptability will be derived as the average of the scores observed at each dose and analysed using a two-way ANOVA.
29	3.2.1.2.10	18JUN2018 (v2.0)	26FEB2020 (v3.0)	The volume taken will also be described. Interaction analysis has been clarified and analysis by country has been added. In addition, analyses by sex, age class and weight class have been added
NA	NA	18JUN2018 (v2.0)	26FEB2020 (v3.0)	New section 3.2.1.3.4 The endpoint "time between the last intake of fluids and the start of colonoscopy procedure" has been added.

6/62

SAP final version 4.0: 25 August 2020

33	3.2.2.1	18JUN2018 (v2.0)	26FEB2020 (v3.0)	Causality of SAEs and TEAEs leading to death have been added in the summary table of AEs. Tables with TEAEs with incidence >= 5 % and with TEAEs by decreasing frequency of PT have been added. The summary table of AEs will also be provided by sex, age class and weight class. 95 % CI of proportions will only be displayed in summary tables, and not in the tables by SOC/PT.
34	3.2.2.2	18JUN2018 (v2.0)	26FEB2020 (v3.0)	As no normal range for sulfate is available, corresponding analyses have been removed. The formula for laboratory data standardisation has been specified.
34	3.2.2.3	18JUN2018 (v2.0)	26FEB2020 (v3.0)	Categories for weight, blood pressure and heart variations have been specified.
34	3.2.2.4	18JUN2018 (v2.0)	26FEB2020 (v3.0)	Tolerability will also be described according to use of nasogastric tube, sex, age class and weight class.
36	3.2.5	18JUN2018 (v2.0)	26FEB2020 (v3.0)	Summaries will also be provided by country.
36	3.2.6	18JUN2018 (v2.0)	26FEB2020 (v3.0)	Demography will also be provided by sex, age class and weight class
38	3.2.8	18JUN2018 (v2.0)	26FEB2020 (v3.0)	All major deviations will be described and not only those having an impact on populations.
40	3.2.15	18JUN2018 (v2.0)	26FEB2020 (v3.0)	Subgroups analyses on country, sex, age class and weight class have been added.

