3.2.1.2.9 Treatment acceptability

The treatment acceptability at the time of intake after dose 1 and after dose 2 will be assessed by a Treatment Acceptability Questionnaire completed by the caregiver or the subject using a

5-point scale questionnaire (see Table 4). It will be tabulated for each dose and overall (by taking the average of the 2 doses then considered as a score as follows: 1= Very badly accepted/unacceptable, 2= Badly but accepted, 3= Neither good nor bad, 4= Well accepted and 5= Very well accepted) by treatment group.

The acceptability for each dose will be assessed using frequency count with two-sided 95 % CI and analysed using Cochran-Mantel-Hænszel (CMH) chi-square for the proportions adjusting for country effect. The row mean scores differ statistic will be used to assess the test significance.

The SAS Freq procedure will be used as follows:

```
proc freq data=ADQS(where=(QSCAT='TREATMENT ACCEPTABILITY
QUESTIONNAIRE' and PARAMCD in ('TRTA011','TRTA012') and ITTFL='Y'));
table COUNTRYC*TRTP*QSORRES / CMH;
by QSGRPID;
```

run;

The p-value of difference will be summarised.

The overall acceptability will be presented by treatment group using descriptive summary statistics (mean, SD, median, quartiles and ranges) and using a two-way ANOVA including treatment and country as well as the interaction between treatment and country, if it is significant (i.e. p < 0.10), as covariates using the following SAS code:

```
proc mixed data=ADQS(where=(QSCAT='TREATMENT ACCEPTABILITY QUESTIONNAIRE' and PARAMCD='TRTA01' and ITTFL='Y'));
```

```
class TRTP COUNTRYC;
model COMPLIPCT = TRTP COUNTRYC TRTP*COUNTRYC;
by ASPID;
```

lsmeans TRTP / diff cl;

run;

The adjusted mean score, the adjusted treatment difference with their 95 % CI and the p-value of difference will be summarised.

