3.2.1.2.10 Treatment compliance

According to the instructions of use provided in the prescription, subjects should get for Eziclen®/Izinova® 750 mL of preparation followed by an additional 750 mL of water at first and second dose, that is to say a total volume of 2250 mL, and for Klean-Prep® 70 mL/kg of preparation according to the weight split into 2 doses with a maximum global volume administered of 4000 mL (2000 mL per dose). The volumes taken will be presented by treatment group using descriptive summary statistics (mean, SD, median, quartiles and ranges). No comparison will be performed since treatment administration schemes are different.

The treatment compliance will be assessed as the percentage of volume of fluid taken relative to the planned volume of fluid to be taken using the volumes of fluids measured by the caregiver and reported in the treatment questionnaire of subject's leaflet during treatment administration by dose and overall for the preparation for Klean-Prep® and for the preparation, the water and the total for Eziclen®/Izinova®. Then the percentage of compliance will be presented by treatment group using descriptive summary statistics (mean,

SD, median, quartiles and ranges) and using a two-way ANOVA including treatment and country as well as the interaction between treatment and country, if it is significant (i.e. p < 0.10), as covariates using the following SAS code:

proc mixed data=ADEX(where=(EXCAT='COMPLIANCE' and EXSCAT='Overall' and ITTFL='Y'));

class TRTP COUNTRYC;

model COMPLIPCT = TRTP COUNTRYC TRTP*COUNTRYC; by ASPID; lsmeans TRTP / diff cl;

run;

The adjusted mean compliances, the adjusted treatment difference with their 95 % CI and the p-value of difference will be summarised.

In addition, this analysis will also be produced per country so that mean compliances and the estimated treatment differences will also be provided per country using the following SAS code.

proc mixed data= ADEX(where=(EXCAT='COMPLIANCE' and EXSCAT='Overall' and ITTFL='Y'));

class TRTP COUNTRYC; model COMPLIPCT = TRTP COUNTRYC TRTP*COUNTRYC; lsmeans TRTP*COUNTRYC / diff cl;

run;

Moreover, this analysis will also be produced per sex, age class and weight class, so that mean compliances and the estimated treatment differences will also be provided per subgroup using the following SAS code and adding the treatment*country interaction if it is significant.

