Appendix 1 Derived data

The following derived data will be calculated:

(1) Treatment group

Treatment groups will be defined as "Eziclen/Izinova" and "Klean-Prep".

(2) Study duration

Study duration (days) will be calculated as (last visit attended - date of informed consent) + 1.

- (3) Successful treatment preparation
- A successful preparation will be derived from a colon cleansing scored as excellent (4) or good (3).
- A failure preparation will be defined as:
 - Fair (2) or poor (1) according to colon cleansing score,
 - Any subject who did not have a colonoscopy based on the investigator's assessment of the cleansing (insufficient faecal output, unclear faecal discharge, etc.) or due to preparation related AEs,
 - Any subject for whom cleaning was not adequate for evaluation,
 - Any subject for whom rescue treatment (saline enema) was needed.

(4) Time to clear effluent

It is defined as the time (expressed in hours) from the first intake of prescription to the first clear watery stool occurrence if any, or to the time of colonoscope introduction, if no clear watery stool is observed before the beginning of the procedure and then the time will be considered as censored for the survival analysis. See section 3.2.1.2.3.

(5) Completion of the procedure

"Yes" if the colonoscopy reached the caecum and the item "Was physician able to reach the caecum?" is "Yes", "No" otherwise.

(6) Duration of the intubation

It is defined as the time (expressed in minutes) from colonoscope introduction to caecal intubation.

(7) Duration of the examination

It is defined as the time (expressed in minutes) from caecal intubation to colonoscope withdrawal.

(8) Need of a rescue treatment

"Yes" if a rescue medication was administered and the item "Was any enema needed to achieve preparation?" is "Yes", "No" otherwise.

(9) Need of a nasogastric tube to complete preparation

"Yes" if a nasogastric tube was inserted and the item "Was a nasogastric tube inserted?" is "Yes" at dose 1 or dose 2, "No" otherwise.

(10) Compliance in percentage

The percentage of compliance is defined as (planned volume - residual volume) / planned volume, adding up the solution and water volume where applicable.

50/62

The planned volume is 750 mL for Eziclen (375 mL per dose), 1500 mL for hydration (750 mL per dose) and 70 mL/kg for Klean-Prep® with a maximum of 4000 mL (maximum 2000 mL per dose).

(11) Compliance with the instructions of use

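### SAP code for nasogastric-tube use and overall acceptability cannot produce the analyses its text describes, and the SAP defines a compliant subject in two ways

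*SAP*

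**What the plan says.** **Nasogastric tube (SAP 3.2.1.2.8).** On tube use and the reason for it, the text says: "They will be tabulated by treatment group using frequency count with two-sided 95 % CI". It adds a CMH test adjusted for country and ends: "The difference of proportions with the 95 % CI and p-value will be summarised". The code given for this opens with "proc freq data=ADEX(where=(EXTRT=' EZICLEN/IZINOVA' and ITTFL='Y" and then requests a country by treatment by tube-use table. Appendix 1, under "9) Need of a nasogastric tube to complete preparation", counts a subject as Yes if a tube was inserted at either dose, with no restriction to one product.

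**Overall acceptability (SAP 3.2.1.2.9).** The text plans a two-way ANOVA of the 1-to-5 score averaged over the two doses. The SAP change log states the same intent: "The overall treatment acceptability will be derived as the average of the scores observed at each dose and analysed using a two-way ANOVA". The code reads "proc mixed data=ADQS(where=(QSCAT='TREATMENT ACCEPTABILITY QUESTIONNAIRE' and PARAMCD='TRTA01' and ITTFL='Y", but its model statement is "model COMPLIPCT = TRTP COUNTRYC TRTP*COUNTRYC", with a BY statement on `ASPID`.

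**Compliance with the instructions of use (SAP 3.2.1.2.10 and Appendix 1).** Section 3.2.1.2.10 sets the Eziclen instructions out as preparation plus water, 2250 mL in total. It then calls a subject compliant if the whole preparation is drunk. Appendix 1 item 11 requires the whole preparation and also all further fluid. SAP 3.2.10 names Appendix 1 as the list of derived data.

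**The concern.** In the first two analyses the code that the SAP says will be used does not do what the text beside it says. The tube filter removes the comparator arm from a comparison of arms. The acceptability model uses the response and BY statement of the compliance analysis, whose code opens "proc mixed data=ADEX(where=(EXCAT='COMPLIANCE' and EXSCAT='Overall' and ITTFL='Y", so it appears to have been carried over from there. Comparing acceptability between arms is a stated secondary objective, and need for a tube is a listed secondary endpoint.

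The compliance wording is a different kind of problem. Either rule runs without an error, so a log check will not show which was used, and checking output against the SAP cannot settle a point on which the SAP disagrees with itself. The two rules can differ in the Eziclen arm only, and the SAP plans a between-arm test and difference on this variable. If the rule is left open, it may be chosen after the results are known.

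**Working it through.** **1. Tube use: what the filter leaves.** CMH general association degrees of freedom = (treatment levels − 1) × (response levels − 1).

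- Both arms present: (2 − 1) × (2 − 1) = 1.
- Eziclen records only: (1 − 1) × (2 − 1) = 0.

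A check on invented counts shows the same. The two countries have, as tube yes/no, Eziclen 5/35 and 4/41, and Klean-Prep 9/31 and 8/37. With both arms the Mantel-Haenszel numerator is −4.0 with variance 5.55. With the Klean-Prep rows removed, both are 0, so no statistic exists. This assumes that no subject randomised to Klean-Prep received Eziclen. The product name in the printed filter also has a leading blank. That may come from text extraction, and nothing here depends on it.

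**2. Acceptability: text against code.**

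| | Text, 3.2.1.2.9 | Code, 3.2.1.2.9 | Compliance code, 3.2.1.2.10 |
|---|---|---|---|
| Data set | Acceptability questionnaire | `ADQS`, acceptability records | `ADEX`, compliance records |
| Response | Mean of two 1-to-5 scores | `COMPLIPCT` | `COMPLIPCT` |
| BY statement | None described | `ASPID` | `ASPID` |

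The acceptability code selects the right records and the wrong response. If `COMPLIPCT` is not in `ADQS`, the program stops with an error; if it is, the wrong variable is analysed. The data set specifications are not shown, so the documents do not say which.

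**3. Compliance: the two rules.** The SAP's own total is reproduced first: 2 × 375 mL preparation + 2 × 750 mL water = 2250 mL, of which 1500 mL is water. Klean-Prep has no separate water volume.

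Take an Eziclen subject who drinks all 750 mL of preparation and a fraction f of the water. Overall compliance = (750 + 1500f)/2250.

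| f | Overall compliance | Compliant, preparation only | Compliant, item 11 |
|---|---|---|---|
| 1 | 100% | Yes | Yes |
| 0.9 | 93.3% | Yes | No |
| 0.5 | 66.7% | Yes | No |
| 0 | 33.3% | Yes | No |

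Let k be the number of Eziclen subjects who finish the preparation but not the water, and assume all 125 planned Eziclen subjects (SAP 1.4.4) are in the ITT population. The Eziclen rate then differs between the rules by k/125, and the Klean-Prep rate by 0. One subject gives 1/125 = 0.8 points. The documents give no value for k; assumed values of 0, 5 and 10 give 0, 4.0 and 8.0 points.

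**The case against.** The first two items are slips in sample code. The prose leaves no doubt about the intended analyses, and neither slip is likely to bias a result unnoticed: one treatment level yields no test, and a missing variable yields an error. SAP 4.3 provides for log checks and for reviewing outputs against the SAP. This largely stands and is why the point is minor. Section 4.3 does, however, require double programming for the primary endpoint only.

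The stronger objection concerns compliance.

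- The conflict may be only verbal. Appendix 1 item 10 adds solution and water where applicable, and 3.2.1.2.10 says preparation and hydration will also be described separately. The main Eziclen figure could therefore be the total volume, in which case the two rules coincide. `ASPID` is not defined in the visible text, so the BY statement does not settle this.
- Naming Appendix 1 as the list of derived data does not give it precedence. It is not fully in step with the body either: item 6 still uses the name duration of intubation, which the change log says was replaced.
- Protocol 1.4 measures compliance in earlier studies by completion of the preparation.

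These points lower certainty about what the authors meant, but the two written definitions still differ. If the body does mean total volume, the shift is zero, which the statement that the rate is raised or left equal already covers. The main support for item 11 is not its place in an appendix. It is that 3.2.1.2.10 itself counts the water as part of the instructions.

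**Conclusion.** All three points hold, at minor severity. Run as printed, the tube code gives no between-arm test or difference, assuming no treatment mix-up. The acceptability code gives no ANOVA of the acceptability score. The compliance definition is worded in two ways; the direction of any effect is known (Eziclen rate higher or equal under the preparation-only wording, Klean-Prep unchanged), but its size cannot be estimated. The 0.8 points per subject rests on 125 Eziclen subjects in the ITT population.

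SAP 3.1.5 makes tests of secondary endpoints descriptive. The primary endpoint, the type I error rate and the sample size are not affected.

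**What to change.** Before analysis:

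- **3.2.1.2.8:** remove the product filter and analyse one record per ITT subject, with tube use set to Yes if a tube was inserted at dose 1 or dose 2, as in Appendix 1 item 9.
- **3.2.1.2.9:** replace `COMPLIPCT` with the acceptability score averaged over the two doses, and drop the BY statement unless it is needed.
- **3.2.1.2.10:** align the sentence defining a compliant subject with Appendix 1 item 11, which matches the instructions set out earlier in that section. No extra table is needed, because preparation and hydration compliance are already to be described separately for Eziclen.

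The cost is two code corrections and one sentence of SAP text, with no new data, table or analysis.
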